2.4 Secondary endpoints

All the secondary supportive efficacy endpoints listed below will be analysed as per protocol section 17.4.

2.4.1 Supportive secondary endpoints

2.4.1.1 Efficacy endpoints

- From Baseline to week 82:
 - Percent of subjects achieving $\geq 5\%$ reduction in baseline BMI at weeks 30, 56 and 82
 - Percent of subjects achieving $\geq 10\%$ reduction in baseline BMI at weeks 30, 56 and 82

- Change in BMI SDS from baseline to 30 and 82 weeks and change from 56 weeks to 82 weeks
- Change from baseline to 30 and 56 weeks in:
 - BMI
 - Body weight (kilogram [kg], pounds [lb] and percent [%])
 - Waist circumference
 - Waist-to-hip circumference ratio
 - Cardiovascular risk factors: high sensitivity C-reactive protein (hsCRP) and fasting lipids: total cholesterol (TC), low density lipoprotein cholesterol (LDL-cholesterol), high density lipoprotein cholesterol (HDL-cholesterol), non-HDL cholesterol, very low density lipoprotein cholesterol (VLDL-cholesterol), triglycerides (TG) and free fatty acids (FFA)
 - Systolic and diastolic blood pressure
 - Glucose metabolism: glycosylated haemoglobin (HbA1c), fasting plasma glucose (FPG), fasting insulin, fasting C-peptide, glycaemic category and homeostasis model assessment of beta-cell function and insulin resistance parameters (HOMA-B and HOMA-IR)
 - Patient reported outcome (PRO) assessed by Impact of Weight on Quality of Life-Kids (IWQOL-Kids)
- Change from 56 weeks to 82 weeks in:
 - BMI
 - Body weight (kilogram [kg], pounds [lb] and percent [%])
 - Waist circumference
 - Waist-to-hip circumference ratio
 - Cardiovascular risk factors: high sensitivity C-reactive protein (hsCRP) and fasting lipids: total cholesterol (TC), low density lipoprotein cholesterol (LDL-cholesterol), high density lipoprotein cholesterol (HDL-cholesterol), non-HDL cholesterol, very low density lipoprotein cholesterol (VLDL-cholesterol), triglycerides (TG) and free fatty acids (FFA)
 - Systolic and diastolic blood pressure
 - Glucose metabolism: glycosylated haemoglobin (HbA1c), fasting plasma glucose (FPG), fasting insulin, fasting C-peptide, glycaemic category and homeostasis model assessment of beta-cell function and insulin resistance parameters (HOMA-B and HOMA-IR)

In addition to all the supportive secondary efficacy analysis following added endpoints will be analysed similarly as per primary endpoint statistical model mentioned in protocol section 17.3.

- Change from baseline to 30 and 56 weeks:
 - BMI SDS (%)

- Glycaemic category will be summarised by frequency count for each treatment group
- Nutritional compliance will be summarised using descriptive statistics for each treatment group.

2.4.1.2 Safety endpoints

Descriptive statistics for all safety endpoints mentioned below will be provided with the aim to compare liraglutide 3.0 mg and placebo. All analyses and tabulations will be done using the safety analysis set. Unless otherwise stated, no formal statistical analyses are planned for the safety endpoints.

- Number of treatment emergent adverse events
- Number of treatment emergent hypoglycaemic episodes:
 - According to ADA/ISPAD classification
 - According to Novo Nordisk/ISPAD classification
- Occurrence of anti-liraglutide antibodies
- Change from baseline to 56 weeks in bone age assessment
- Change from baseline to 30 and 56 weeks in:
 - Pulse
 - Electrocardiogram (ECG)
 - Laboratory parameters:
 - Haematology: haemoglobin, haematocrit, thrombocytes, erythrocytes, leucocytes, differential count (eosinophils, neutrophils, basophils, lymphocytes, monocytes)
 - Biochemistry: creatinine, creatinine kinase, urea (BUN), albumin, bilirubin (total), alanine aminotransferase (ALT), aspartate aminotransferase (AST), alkaline phosphatase (ALP), sodium, potassium, calcium total, calcium, albumin-corrected, amylase, lipase, and carcinoembryonic antigen (CEA)
 - Hormone levels: calcitonin, insulin-like growth factor-1 (IGF-1), thyroid stimulating hormone (TSH), free thyroxine (free T4), dehydroepiandrosterone sulfate (DHEAS), luteinising hormone (LH), follicle stimulating hormone (FSH), estradiol (females), testosterone (males), prolactin, adrenocorticotrophic hormone (ACTH), cortisol
 - Bone metabolism markers: Type 1 collagen N-telopeptide (NTX1), type 1 C-telopeptide (CTX1), procollagen 1 N-terminal propeptide (P1NP), alkaline phosphatase (bone)
 - Pubertal status
 - Physical examination
 - Height standard deviation score (SDS)
 - Mental health assessed by Columbia Suicidality Severity Rating Scale (C-SSRS) and Patient Reported Health Questionnaire 9 (PHQ-9)

- Change from 56 weeks to 82 weeks in:
 - Pulse
 - Laboratory parameters:
 - Haematology: haemoglobin, haematocrit, thrombocytes, erythrocytes, leucocytes, differential count (eosinophils, neutrophils, basophils, lymphocytes, monocytes)
 - Biochemistry: creatinine, creatinine kinase, urea (BUN), albumin, bilirubin (total), alanine aminotransferase (ALT), aspartate aminotransferase (AST), alkaline phosphatase (ALP), sodium, potassium, calcium total, calcium, albumin- corrected, amylase, lipase, and carcinoembryonic antigen (CEA)
 - Hormone levels: calcitonin, insulin-like growth factor-1 (IGF-1), thyroid stimulating hormone (TSH), free thyroxine (free T4), dehydroepiandrosterone sulfate (DHEAS), luteinising hormone (LH), follicle stimulating hormone (FSH), estradiol (females), testosterone (males), prolactin, adrenocorticotrophic hormone (ACTH), cortisol
 - Bone metabolism markers: Type 1 collagen N-telopeptide (NTX1), type 1 C-telopeptide (CTX1), procollagen 1 N-terminal propeptide (P1NP), alkaline phosphatase (bone)
 - Pubertal status
 - Physical examination
 - Height standard deviation score (SDS)
 - Patient Reported Health Questionnaire 9 (PHQ-9)

2.5 Endpoint derivation methods

2.5.1 BMI Standard deviation score (BMI SDS) and Height Standard deviation score (Height SDS)

BMI SDS and height SDS score will be calculated using external reference data on BMI and height from WHO⁴

The following procedure is recommended to calculate a z-score for an individual child with measurement y at age t :

1: Calculate

$$Z_{\text{ind}} = \frac{[y/M(t)]L(t) - 1}{S(t) L(t)}$$

2 : Compute the final z-score (Z_{ind}^*) of the child for the indicator as:

$$z_{ind}^* = \begin{cases} z_{ind} & \text{if } |z_{ind}| \leq 3 \\ 3 + \left(\frac{y - SD3pos}{SD23pos} \right) & \text{if } z_{ind} > 3 \\ -3 + \left(\frac{y - SD3neg}{SD23neg} \right) & \text{if } z_{ind} < -3 \end{cases}$$

Where:

- L(t), M(t) and S(t): Box-cox power, median and CV respectively
- y: Individual BMI or height value
- SD3pos: is the cut-off 3 SD calculated at t (age) by LMS method:
 $SD3pos = M(t)[1 + L(t) * S(t) * (3)]^{1/L(t)}$
- SD3neg : is the cut-off -3 SD calculated at t by the LMS method:
 $SD3neg = M(t)[1 + L(t) * S(t) * (-3)]^{1/L(t)}$
- SD23pos : is the difference between the cut-offs 3 SD and 2 SD calculated at t by LMS method:
 $SD23pos = M(t)[1 + L(t) * S(t) * (3)]^{1/L(t)} - M(t)[1 + L(t) * S(t) * (2)]^{1/L(t)}$
- SD23neg : is the difference between the cut-offs -2 SD and -3 SD calculated at t by LMS method:
 $SD23neg = M(t)[1 + L(t) * S(t) * (-2)]^{1/L(t)} - M(t)[1 + L(t) * S(t) * (-3)]^{1/L(t)}$

To illustrate the procedure, an example with BMI-for-age for boys is provided below and displayed in [Figure 1](#).

[figure not shown]

Figure 1 Examples of children/adolescents ranked according to the 2007 WHO BMI-for-age reference.

Child 1: 11 year-old boy with BMI=30

$L=1.7862$ $M=16.9392$ $S=0.11070$

$$Z = \frac{[30.0/16.9392]^{(-1.7862)} - 1}{0.11070 * (-1.7862)} = 3.24 > 3$$

$$SD3 = 16.9392 * [1 + (-1.7862) * 0.11070 * (3)]^{1/(-1.7862)} = 28.03$$

$$SD2 = 16.9392 * [1 + (-1.7862) * 0.11071 * (2)]^{1/(-1.7862)} = 22.45$$

$$SD23 = 28.03 - 22.45 = 5.58$$

$$Z_{ind}^* = 3 + (30 - 28.03/5.58) = 3.35 \text{ (BMI SDS)}$$

Similar calculation will be done for height SDS.

2.5.2 IWQoL-Kids

The impact of weight on Quality of Life-Kids for Clinical Trials Version contains 27 questions with categorical answers (never, rarely, sometimes, usually, always). All these 27 questions are categorised into 4 domains (Physical Comfort, Body Esteem, Social Life, Family Life) scores. The Total score is the sum of all the 4 domain scores.

Table 2-5: Composite scores

Composite score	Items	Total number of items
Physical Comfort	1 - 6	6
Body Esteem	7 - 15	9
Social Life	16 - 21	6
Family Life	22 - 27	6
Total	1 - 27	27

The derivation of the composite scores within the ADQSIWQL dataset can be done in several ways, but below procedure was followed on this trial.

The categorical values of the questionnaire are converted into numbers (in ADQSIWQL) as below:

Table 2-6: Conversion of categorical values to numeric values

	Categorical values	Numeric values
Items 1- 27		
	Never True	1
	Rarely True	2
	Sometimes True	3
	Usually True	4
	Always True	5

The maximum and minimum possible score for each item will be 5 and 1, respectively. Composite score will be calculated for all four domains, including a total composite score will be calculated including all the domains.

For all four composite scores, at least 50% of the questions within a composite should be answered to calculate the score. For the total score, at least 75% of the 27 items should be answered.

The algorithm used for the derivation of a composite score (per subject and per visit):

$$((T*S_{max}) - (T*C_{avg})) / ((T*S_{max}) - (T*S_{min})) * 100\%$$

where,

T is the total number of items in the composite score (see [Table 2-5](#)).

C_{avg} is the average score of the composite (for subject X at visit X).

S_{max} is the maximum possible score value (5).

S_{min} is the minimum possible score value (1).

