8.3.3 Patient-reported outcome questionnaire, IWQOL-Kids

The Impact of Weight on Quality of Life-Kids (IWQOL-Kids) is a disease-specific questionnaire which measures the impact of weight on quality of life in adolescents and is validated in youth ages 11 years and older⁴⁶. The four concepts captured are:

- the impact of weight on an individual’s physical mobility and comfort (Physical Comfort)
- how an individual feels about themselves and their body (Body Esteem)
- how an individual is treated in their social environment (Social Life)
- the individual’s perception of what family members may think and feel about them (Family Life).

The questionnaire has 27 items and a total, as well as domain-specific score(s), can be derived. The scaled scores range from 0–100, with higher scores representing better health-related quality of life.

The questionnaire is a self-administered questionnaire. It must be completed by the subject using an electronic device; see Section [13.3](#), and it must be completed without assistance of the investigator or delegated staff.

At fasting visits, the questionnaire should be completed after all fasting-related activities, but before any other visit-related procedures are conducted. Only subjects can make changes in the questionnaire.

After completion, the questionnaire must be reviewed by the investigator or delegated staff on the same day for potential AEs, including any overall change in health and concomitant medication. When reviewing the questionnaires, the investigator should not influence or question the subject on the content of the subject’s response to the questionnaire questions. Review of questionnaires must be documented in the subject’s medical record.

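### SAP 2.5.2 describes the IWQOL-Kids total in two ways that do not agree: a sum of four domain scores, and a 0–100 score on all 27 items

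*SAP*

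**What the plan says.** Protocol 8.3.3 introduces the instrument: "The questionnaire has 27 items and a total, as well as domain-specific score(s), can be derived". On the scale it says: "The scaled scores range from 0–100, with higher scores representing better health-related quality of life".

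SAP 2.5.2 opens with the domain structure, "All these 27 questions are categorised into 4 domains (Physical Comfort, Body Esteem, Social Life, Family Life) scores", and follows it directly with "The Total score is the sum of all the 4 domain scores". It does not say whether the domain scores to be added are raw or scaled, and it gives no range for the sum.

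The rest of the same section describes the total differently:

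- Table 2-5 lists Total as a composite in its own right, covering items 1 to 27.
- The text allows that composites can be derived in more than one way, "but below procedure was followed on this trial".
- It then states: "Composite score will be calculated for all four domains, including a total composite score will be calculated including all the domains".
- The total has its own completeness rule: "For the total score, at least 75% of the 27 items should be answered". A domain needs only half of its items.
- One algorithm is printed for a composite score, in which "T is the total number of items in the composite score", read from Table 2-5.

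The score is analysed as change from baseline at weeks 30 and 56 by ANCOVA with multiple imputation (Protocol 17.4.1.1; SAP Table 2-4, row 8). Both places refer only to a PRO score and do not name the total or its scale.

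**The concern.** One section gives two rules for one derived variable. The algorithm is the only place where a domain score is defined, and it produces a 0–100 score. Adding four such scores gives a different variable from the 27-item total: its range is four times as wide, its domain weights differ, and it needs different data to be computable.

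The section's vocabulary leaves some room for the wrong choice. Table 2-5 and the sentence on the total composite count the total among the composites. The completeness rule, however, sets the four composites apart from the total. A programmer could read the algorithm as applying to the four domains only and take the total from the summing sentence.

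At stake are the size and comparability of the reported mean changes in a measure named in the secondary objectives (Protocol 4.1), and possibly its p-value.

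**Working it through.** **Inputs (SAP 2.5.2).** Item scores run from Smin = 1 to Smax = 5. The domains have 6, 9, 6 and 6 items (Physical Comfort, Body Esteem, Social Life, Family Life), 27 in all. At least 50% of items are needed for a domain and at least 75% of 27 for the total.

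**The algorithm.** Score = (T×5 − T×Cavg) / (T×5 − T×1) × 100. T cancels, leaving (5 − Cavg)/4 × 100. What separates the total from a domain is therefore that Cavg is averaged over all 27 items.

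**Reproducing the protocol's range.**

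| Cavg | Each domain | 27-item total | Sum of four scaled domains |
|---|---|---|---|
| 1 | 100 | 100 | 400 |
| 3 | 50 | 50 | 200 |
| 5 | 0 | 0 | 0 |

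The algorithm gives 0–100, as the protocol states. The literal sum gives 0–400.

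**Weights, all items answered.** The 27-item total is the item-weighted mean of the domain scores: 9/27 = 33.3% for Body Esteem and 6/27 = 22.2% for each other domain. The sum weights each domain 25%.

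**Effect on a change score.**

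- Every domain +10: the total moves 10 and the sum 40 (ratio 4).
- Body Esteem alone +10: 9/27 × 10 = 3.33 against 10 (ratio 3).
- One six-item domain alone +10: 6/27 × 10 = 2.22 against 10 (ratio 4.5).

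If all domains move in the same direction, the sum overstates the change by a factor between 3 and 4.5.

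**Worked level (illustrative means, not from the documents).** Item means of 2.0, 3.0, 1.5 and 1.2 give domain scores of 75, 50, 87.5 and 95.

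- Sum: 75 + 50 + 87.5 + 95 = 307.5.
- 27-item total: item sum 6×2.0 + 9×3.0 + 6×1.5 + 6×1.2 = 55.2; (5 − 55.2/27)/4 × 100 = 73.9.
- Sum divided by 4: 76.9, so rescaling does not recover the total.

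A one-point improvement on every Body Esteem item adds 25 to the sum and 9/(27×4) × 100 = 8.3 to the total.

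**Who has a score.** 75% of 27 is 20.25, so 21 items are needed.

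- One six-item domain wholly missing: 21/27 = 77.8% answered. The 27-item total exists; the four-domain sum lacks a term.
- Exactly half of each domain answered, rounded up: 3 + 5 + 3 + 3 = 14 items, or 51.9%. All four domains can be scored, but the total fails the 75% rule. The sum would be reported only if that rule were dropped along with the algorithm.

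**Effect on the test.** Multiplying outcome and baseline by 4 multiplies the estimate and its standard error by 4, so the p-value is unchanged. The sum, however, is 4 times an equally weighted mean, not 4 times the item-weighted mean. The difference in weights and in missing-item handling can move the p-value.

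**The case against.** The strongest reply is that the section already settles the matter. It says which procedure was followed, and that procedure includes the total: it has its own row in Table 2-5, its own completeness rule, and the one printed algorithm with T read from that table. The result is 0–100, as in the protocol. To go wrong, a programmer would have to set all of this aside. This largely stands, and it makes the harm conditional.

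A second reply is that the summing sentence comes before any scaling is introduced and may mean raw domain sums. Those add up to the 27-item raw sum, 27 to 135, and (135 − raw sum)/108 × 100 reproduces the algorithm exactly when all items are answered. This reading is possible. But the section never defines a raw domain score, and the raw sum runs in the opposite direction, higher being worse. On this reading the sentence describes an unscaled intermediate and still not the 0–100 total.

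A third reply is that partial questionnaires should be rare, because Protocol 13.3 describes built-in edit checks on the electronic device meant to ensure that all relevant questions are answered. That limits the missing-item effect but not the difference in scale or weights.

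A reader might infer that the SAP defines the total on 0–400, or that the reported IWQOL-Kids result will be inflated about fourfold. The documents support neither. The 0–400 range is printed nowhere, and the stated procedure points to the 27-item score.

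**Conclusion.** The inconsistency is real and minor. The summing sentence, read with the only domain score the section defines, conflicts with Table 2-5, the 75% rule, the algorithm and Protocol 8.3.3. The algorithm appears to be the operative rule, and on that basis the endpoint is correctly specified at 0–100.

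If the sentence were programmed instead, changes would read 3 to 4.5 times too large when the domains move together. Body Esteem would fall from 33.3% to 25% of the weight, each other domain would rise from 22.2% to 25%, and some subjects with missing items would move between scored and unscored.

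This rests on domain scores meaning scaled scores. The effect on the p-value cannot be sized from the documents, since it depends on how the treatment effect differs across domains and on how many items are missing. The measure is a supportive secondary endpoint without the asterisk that Protocol 4.2.2 uses for key disclosure endpoints. The primary analysis, sample size and superiority claim do not depend on it.

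**What to change.** In SAP 2.5.2, replace the summing sentence with: *The Total score is derived from all 27 items with the algorithm below (T = 27) and ranges from 0 to 100.* Because T cancels in the formula, it would help to add that Cavg for the total is the mean over the items 1 to 27 that were answered.

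Then confirm that the total in the ADQSIWQL dataset was derived this way; a total above 100 for any subject would show that it was not.

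The cost is one sentence and one check of a derived variable. No data collection, sample size or analysis model changes.

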2.5.3 C-SSRS questionnaire

The Columbia-Suicide Severity Rating Scale questionnaire is used to assess the subject's mental state. It contains two sets of questions; one meant for the screening/randomisation visit (C-SSRS-01; baseline) and the other for the rest of the visits (C-SSRS-02; since last visit). At screening/randomisation, the questionnaire is part of the exclusion criteria (suicidal behaviour, previous suicide attempts). During the trial, the questionnaire is used to evaluate the subject's mental status between visits. The first part of the questionnaire is to build up around 'yes/no' questions, which depending on the answers trigger other parts of the questionnaire

2.5.4 PHQ-9 questionnaire

The Patient Health Questionnaire 9 is used to assess the mental health of the subject. PHQ-9 is done throughout the trial period. It contains 9 questions which are answered with a categorical rating (not at all, several days, more than half the days, nearly every day) translated directly into a number (0-3). The numbers are summed at the bottom of the questionnaire by the investigator. Similar to C-SSRS-01, this questionnaire is used at screening/randomisation as part of the exclusion criteria, i.e., if the total score is ≥ 15 then the subject should be excluded from the trial.

2.6 Pharmacokinetic and Pharmacodynamic modelling

The Pharmacokinetic and pharmacodynamic analysis will be done as mentioned in the protocol section 17.5.

2.7 Reporting Endpoints

All the continuous endpoints mentioned in section [2.2](#) and [2.4](#) will be summarised by treatment group for in-trial period using descriptive statistics such as mean, SD, 5th percentile and 95th percentile, minimum and maximum.

Lipids will be summarised by treatment group using descriptive statistics such as mean, geometric mean, SD, CV, 5th percentile and 95th percentile, minimum and maximum except HbA1c and FPG which will be summarised as rest of the continuous endpoints.

For the categorical endpoints mentioned in section [2.2](#) and [2.4](#) will summarised by treatment group using frequency counts and percentage by treatment groups.

3 Changes to the statistical analyses planned in the protocol

In this SAP the following changes is been made to the statistical consideration in the protocol are as elaborated below for:

3.1 Primary endpoint

- Primary analysis will be performed on in-trial period.
- Tanner stage and glycaemic category collected at randomisation visit will be considered as fixed effect while performing ANCOVA for change from baseline to week 56.
- Tanner stage for each subject at baseline is been derived and grouped using the information received from eCRF.

3.2 Supportive secondary efficacy endpoints

- All the secondary supportive analysis will be performed on in-trial period.
- To analyse the change in BMI SDS from week 56 to week 82 subjects who have completed the treatment (treatment completers), only their assessment at week 56 will be considered as baseline. No change from week 56 to 82 will be calculated for treatment discontinued subjects and for withdrawn subjects unless they have week 56 visit assessment collected.
- Multiple imputation will not to be considered for change in BMI SDS from week 56 to 82 parameter if there is no missing assessment.
- Tanner stage and glycaemic category collected at randomisation visit will be considered as fixed effect while performing ANCOVA for change from baseline to week 30, 56 and 82 and change from week 56 to 82.
- For “percentage of subjects achieving $\geq 5\%$ reduction” and “Percentage of subjects achieving $\geq 10\%$ reduction” in baseline BMI at week 30, 56 and 82. Missing imputation will be handled as mentioned in section [2.3](#) with the baseline BMI as covariate instead of baseline BMI SDS.
- Body weight with standard units (Kg) will only be used in all summary and analysis outputs.

Below additional supportive secondary endpoint is been included in section [2.4](#)

- Change from baseline to 30 and 56 weeks in:
 - BMI SDS (%)

3.3 Supportive secondary safety endpoints

- For overall tanner staging, the maximum scale irrespective of the categorical question will be considered.
- For adverse events in run-in period all the subjects who has attended at least one run-in visit will be included in the run-in outputs.
- C-SSRS will only be summarised using summary statistics (frequency count, percentage) for screening, baseline, week 30, week 56 and week 82 and the shift from baseline to 30 and 56 week and from week 56 to 82 will not be produced.
- Only standard units will be reported for all laboratory parameters.

- Boxplots will not be produced for laboratory parameters.
- ECG and bone age assessment will be summarised using summary statistics (frequency count, percentage) by treatment group for each visit will be produced. Shift table will be produced for ECG at week 30 and week 56.
- SAS will be used to analyse change from baseline pulse values at week 30 and 56.

The following text in protocol:

“Bone age assessment at baseline and change in bone age assessment will be summarised using descriptive statistics”

is replaced to:

“Bone age assessment is summarised using frequencies count and percentages. A shift table will be provided for change in baseline to week 56.”

